### 3.7 Analysis of the primary outcome

The primary outcome of the mRS at 90 days will be analysed as an ordinal variable with 7 levels. The primary intervention effect will be estimated as the OR of a higher mRS between the intervention arm and the control arm obtained from an ordinal logistic model (defined below).

#### 3.7.1 Main analysis

To account for stratification by site and to maximise power, the main analysis will be performed using ordinal logistic regression with treatment allocation as a fixed effect, site as a random effect, and time from onset and baseline NIHSS as fixed covariates. The effect of the intervention will be presented as the OR of a worse outcome and its 95% CI using the control arm as the reference (i.e., where an OR greater than unity corresponds to an increase in mRS in the intervention arm compared to the control arm).

We will test the proportional-odds assumption using a score test. In case of violation, we will still proceed with the analysis and interpret the intervention OR as an average effect across all mRS levels but with the understanding that it may not be constant across all levels. This will be complemented by a graphical assessment of shifts across categories using bar plots as well as a binary analysis (see Section 3.8.1). As a sensitivity analysis, we will apply partial proportional odds logistic regression, relaxing the proportional odds assumption for covariates where it does not hold.

#### 3.7.2 Adjusted analyses

Adjusted analyses will be performed by adding the following covariates to the main ordinal logistic regression model: country of recruitment (if multiple countries), mRS before stroke (categorical), age (continuous), sex (male vs female). The adjusted treatment effect will be reported as the adjusted OR and 95% CI. As for the main analysis, in case of violation of the proportional odds assumption, we will perform both a full proportional odds model as well as a partial proportional odds model for covariates violating the assumption.

#### 3.7.3 Subgroup analyses

Ten pre-specified subgroup analyses will be carried out, irrespective of whether there is a significant treatment effect on the primary outcome. Subgroups are defined as follows:

- Age (<65 vs 65 or more)
- Sex (male vs female)
- Onset time to recanalisation (<6 vs ≥6 hours)
- Baseline systolic and diastolic BP (above vs below median)
- History of hypertension (yes vs no)
- Ethnicity (Asian vs other), only if recruitment outside of China

- Presumed aetiological subtype (intracranial atherosclerosis vs extracranial atherosclerosis vs cardioembolism vs dissection/other)
- Baseline NIHSS (above vs below median)
- TICI score after EVT (2b vs 3)
- Occlusion site (anterior circulation vs. posterior circulation)
- IV thrombolysis administered (yes vs no)

The analysis for each subgroup will be performed by adding the subgroup variable as well as its interaction with the intervention as fixed effects to the main logistic regression model (see Section 3.7.1). Within each subgroup, summary measures will include raw counts and percentages within each treatment arm, as well as the OR for treatment effect with a 95% CI. The results will be displayed on a forest plot, including the p-value for heterogeneity corresponding to the interaction term between the intervention and subgroup variable.

#### **3.7.4 Treatment of missing data**

The proportion of data missing for the primary outcome (mRS at 90 days) will be described while blinded to the intervention. In case of non-negligible amounts of missing data (>5%), we will use controlled multiple imputations to assess under what conditions the results change, and how plausible these conditions are, using the approach described by Cro et al.

We will first run an imputation model under the missing at random (MAR) assumption. This MAR imputation model will use fully conditional specification (FCS) and will include the following variables: mRS at 90 days, the NIHSS at 7 days (or hospital discharge, if sooner), a variable indicating the intervention, and all key socio-demographic, clinical, and medical baseline variables. The mRS at 7 or 90 days and NIHSS at 7 days will be imputed using an ordinal logistic model. Other variables will be imputed using either linear regression (for continuous/ordinal variables) or a discriminant function method (for nominal variables). One hundred sets of imputed data will be created and analysed using the model described in Section 3.7.1. Estimates of the treatment effect ( $e^{\theta}$  in Model 1) and its standard errors will be combined to obtain a pooled common OR and 95%CI.

Using the same 100 sets of imputed data as our base, we will then assume different mRS levels for subjects who had missing mRS data at 90 days and had their mRS value imputed. We will assume that those with a missing mRS were more likely to have a poorer outcome than those with a non-missing mRS; we will therefore add 1 to their imputed mRS score (with a maximum score of 6 for those with no vital status available or a maximum score of 5 for those known to be alive). We will then analyse the 100 modified-imputed dataset and combine the results using the same strategy as for the base set of imputed data. As an additional sensitivity analysis, we will impute all missing mRS score at 90 days with the worst possible score (i.e. a score of 6 for those with unknown vital status and a score of 5 for those known to be alive but with a missing mRS).

While this assumption is unlikely to hold in most cases, it is plausible that some subjects may have become uncontactable due to death or serious deterioration after hospital discharge.

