## 3.2 Data sets analysed

**Intention-to-treat (ITT) population:** The ITT population will consist of all patients randomised regardless of whether they received the allocated intervention. This will be used as the basis to assess both efficacy and safety.

**Efficacy analysis set:** The main analysis set will consist of all patients in the ITT population with a non-missing primary outcome (i.e. those who are known to have died or with mRS cores at 90 days). In case of missing data leading to exclusion from the ITT population, sensitivity analyses will be performed (see Section 3.7.4).

**Per-protocol (PP) analysis set:** The PP set will consist of patients from the efficacy analysis who did not have a relevant protocol violation, defined as any of: age <18 years; final diagnosis not AIS; SBP <140 mmHg (inclusion criteria BP level); EVT undertaken >24 hours; EVT did not achieve reperfusion (eTICI score <2b); and failure to obtain a blind assessment of the 90-day outcome. The per-protocol set will be applied as a sensitivity analysis.

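### The base multiple imputation in SAP 3.7.4 ignores known day-90 survival, so some patients known to be alive are imputed as dead and the check only partly corrects uneven loss of survivors

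*SAP*

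**What the plan says.** SAP 3.7 treats the 90-day mRS as "analysed as an ordinal variable with 7 levels"; level 6 is death. SAP 3.2 limits the main analysis to patients with a non-missing outcome, described as "those who are known to have died or with mRS cores at 90 days". A death always counts, but a survivor counts only if an mRS was obtained.

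If more than 5% of primary outcomes are missing, SAP 3.7.4 runs three further analyses.

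- **Base step, missing at random.** Fully conditional specification with 100 data sets. The listed variables are "mRS at 90 days, the NIHSS at 7 days (or hospital discharge, if sooner), a variable indicating the intervention" and key baseline variables. On method: "The mRS at 7 or 90 days and NIHSS at 7 days will be imputed using an ordinal logistic model". Nothing here concerns patients whose survival is known.
- **+1 step.** This starts from the 100 base data sets and assumes that missing patients did worse, so each imputed score is raised by one level. Only at this point does a limit that depends on vital status appear: "with a maximum score of 6 for those with no vital status available or a maximum score of 5 for those known to be alive".
- **Worst score.** Missing values become 6 if vital status is unknown and 5 if the patient is known to be alive.

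**The concern.** The SAP recognises patients who are known to be alive but have no mRS, and it limits them to 5 in two of the three steps. The step without that limit is the one on which the +1 step is built. A programmer following the text would draw these patients from all seven levels, and some would come out as deaths that are known not to have happened.

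The analysis is meant to test the complete-case result. That result over-represents deaths whenever known survivors are lost, and an imputation model fitted to the same data without vital status tends to reproduce the excess. If one arm loses more known survivors than the other, the imputed OR stays shifted in the same direction as the complete-case OR, and the two can agree for the wrong reason. Allocation is open-label, so uneven loss is a reasonable condition to test.

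**Working it through.** **Inputs.** Control mRS distribution for 0 to 6 (SAP 2.5): 10.0, 16.9, 19.1, 16.9, 15.6, 6.2, 15.3%. N = 2257, design OR 0.77, two-sided alpha 4.82%, power 90%, allocation 1:1. The documents do not give the missingness rates, the share of missing patients known to be alive, or the share of deaths by day 7. Those used below are assumptions.

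**The plan's own figure.** The Whitehead formula N = 12(z_α/2 + z_β)² / [(ln OR)²(1 − Σp̄³)], with z = 1.976 and 1.282 and Σp̄³ = 0.0257, gives 1913. Dividing by 0.95 for loss and by 0.95² for drop-in/drop-out gives 2231, which is 1.2% below 2257. The distribution is therefore a sound basis for illustration, and no stated figure is disputed.

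**Impossible deaths per imputed data set.** Take 6% missing, 0.06 × 2257 = 135 patients, all known alive.

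- From the planning distribution: 0.153 × 135 ≈ 21. From the observed data, where the death share has risen to 0.153/0.94 = 16.3%: about 22.
- If day-7 death is coded and used as a predictor, draws come from patients alive at day 7. With 30% of deaths by day 7, the share drawn as 6 is 0.153 × 0.7 / (0.94 − 0.153 × 0.3) = 12.0%, about 16 patients. With 70% it is 0.153 × 0.3 / (0.94 − 0.153 × 0.7) = 5.5%, about 7 patients.
- The counts fall in proportion if only some missing patients are known alive.

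**Effect on the OR.** Remove survivors at random at the stated rate, complete each arm's expected table by the rule, and fit logit P(mRS ≥ k) = α_k + β × arm. At 3%/7% missing (control/intensive) the observed death shares are 0.153/0.97 = 15.8% and 0.153/0.93 = 16.5%, although the true share is 15.3% in both arms. Without predictors, imputation reproduces those shares.

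| Missing (control/intensive), no true effect | Complete case | Base step as written, no predictors | As written, day-7 death used (70% to 30% of deaths by day 7) | Restricted to 0-5 |
|---|---|---|---|---|
| 6%/6% | 1.000 | 1.000 | 1.000 | 1.000 |
| 3%/7% | 1.021 | 1.021 | 1.007 to 1.016 | 1.000 |
| 3%/9% | 1.033 | 1.033 | 1.011 to 1.024 | 1.000 |

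At 9%/3% the no-predictor figure is 0.97. With a true OR of 0.77 and no predictors, the base step gives 0.768 at 6%/6% and 0.783 at 3%/7%; the restricted draw gives 0.770 in both. With 1:1 allocation, 3%/7% averages 5%, at the SAP's trigger and not above it; 3%/9% averages 6%.

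For scale, the SE of the log OR is √[12 / (2257 × 0.94 × (1 − 0.0252))] = 0.076. ln 1.033 = 0.032 is about 0.4 SE.

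**The +1 step for a known survivor.** Draws of 0-4 rise by one, 5 stays at 5, and 6 becomes min(7, 5) = 5.

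- Mean of an admissible 0-5 base: (16.9 + 2×19.1 + 3×16.9 + 4×15.6 + 5×6.2)/84.7 = 199.2/84.7 = 2.35.
- Mean after +1 as written: (1×10.0 + 2×16.9 + 3×19.1 + 4×16.9 + 5×(15.6 + 6.2 + 15.3))/100 = 3.54, a shift of +1.19 from the admissible base.
- Intended shift, +1 applied to that base: 78.5/84.7 = +0.93.
- Share ending at 5: 15.6 + 6.2 + 15.3 = 37.1% as written, against (15.6 + 6.2)/84.7 = 25.7%.

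At 3%/7% with no true effect and no predictors, the +1 OR is 1.047 as written and 1.036 from a restricted base.

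**The case against.** The strongest reply is that this matters little. Imputation runs only above 5% missing. The SAP's stated worry is patients who cannot be contacted because they died or deteriorated; their vital status is unknown, and a draw of 6 is legitimate. Day-90 information may come from the patient, a caregiver or a doctor (SAP Table 18), so patients known to be alive with no mRS may be few. With balanced loss the OR bias is nil or negligible. The imputation model has predictors: day-7 NIHSS has a death level in SAP 3.8.3, and 3.7.4 mentions a day-7 mRS. Exact equality of complete-case and imputed ORs arises only when no predictor carries information on survival.

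All of this stands as a limit on size. It does not remove the fault. SAP 3.7.4 does not say whether the day-7 death coding is used, and no day-7 variable can rule out a drawn death after day 7 in a patient known to be alive at day 90.

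A reader might also infer that the +1 step moves known survivors in the wrong direction, because a 6 becomes a 5. Measured from the drawn values, the mean shift is 0.785 − 0.153 = 0.63. That baseline includes the impossible deaths. Against an admissible base the step overshoots towards worse outcome, and no known survivor ends above 5. The documents do not support the claim that it is too mild or reversed.

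**Conclusion.** The point holds as a specification error in a conditional sensitivity analysis. The base step discards known survival, creates deaths known not to have occurred, and only partly corrects the complete-case selection when loss of known survivors differs by arm. On the assumed rates the OR is off by roughly 1 to 3%, under half a standard error; with equal loss the bias is negligible. The +1 step inherits the fault as an overshoot and a pile-up at 5. The rule does not alter the primary estimate, and the worst-score analysis handles known survivors correctly.

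A reader might go further and infer that the imputed result simply repeats the complete-case bias, or that the trial's conclusion is at risk. The first is exact only without informative predictors. The second is not shown by anything in the documents. The correction is still worth making, because these analyses exist to show when the result would change.

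**What to change.** In SAP 3.7.4:

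1. State that the missing-at-random analysis uses known day-90 vital status.
2. For patients known to be alive at day 90, impute mRS from an ordinal model fitted in survivors and restricted to 0-5.
3. Draw from 0-6 only when vital status is unknown.
4. Apply +1 to that base, capped at 5 or 6 as now.

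Stating whether the day-7 NIHSS enters the imputation with its death level would settle a related ambiguity.

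The cost is a few sentences and a small addition to the imputation code: a survivor-only model within the fully conditional specification. The vital-status information is already needed for the existing caps. The primary model and the sample size do not change.

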### **3.7.5 Per-protocol analyses**

The main model (section 3.7.1) as well as the adjusted analyses (section 3.7.2) will be repeated in the PP population as defined in Section 3.2.

## **3.8 Analysis of secondary outcomes**

All secondary outcome analyses described in this section will be performed in the efficacy (primary) and PP (sensitivity) analyses sets as defined in Section 3.2.

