### 2.4.2 Secondary outcomes

- Intracerebral haemorrhage (ICH), assessed by CT imaging and adjudicated centrally according to five possible definitions:
  - a) symptomatic ICH (sICH), based on National Institutes of Neurological Diseases and Stroke (NINDS) criteria of brain imaging (or necropsy) confirmed ICH with  $\geq$ 1 points deterioration in NIHSS score or death within 36 hours from baseline
  - b) sICH, defined by Safe Implementation of Thrombolysis in Stroke-Monitoring Study (SITS-MOST) criteria, as large ('type II') parenchymal ICH with  $\geq$ 4 points decline in NIHSS score or death within 36 hours from baseline
  - c) sICH, defined by the new Heidelberg Bleeding Classification (HBC) criteria, the details of which are outlined in Appendix 1. *This will be the primary safety measure.*
  - d) ICH of any type in brain imaging  $\leq$ 7 days of treatment

- e) any sICH after EVT within 90 days
- Imaging outcomes
  - a) infarct size assessed by any form of brain imaging (MRI or CT) at 48±24 hours
  - b) oedema size assessed by MRI or by CT during days 2-7
- Death or dependency, measured by NIHSS at 7 days
- The followings at 90 days:
  - Death or major disability (mRS 0-2 vs mRS 3-6)
  - Death and disability as separate categories (mRS 0-2 vs mRS 3-5 vs mRS 6)
  - Health-related quality of life (HRQoL) using EuroQoL EQ-5D-3L scale
  - Duration of hospitalisation
  - Residence
  - Hospital service cost (part of separate health economic analysis)

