### **3.8.2 ICH outcomes**

ICH is defined according to 5 definitions (see Section 2.4.2) but the primary measure will be with the Heidelberg criteria. These will be reported as the number and proportion of subjects experiencing an event. The effect of the intervention will be estimated using the same approach as in the binary analysis of mRS (see Section 3.8.1). We will apply the covariate adjustments described in Section 3.7.2; however, no subgroup or imputed analysis will be performed on this outcome.

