### **3.8.4 Imaging endpoints**

Infarct and oedema size will be analysed using linear mixed models with the same fixed and random effects as the main outcome analysis. Given that baseline measurements may not be available for all patients, we will use a constrained longitudinal data analysis (cLDA) model with both the baseline value and the follow-up value included as outcomes. The cLDA model constraints the mean baseline values to be equal between the two arms, which is a plausible assumption in a randomised trial. This approach has the advantage that any patient with at least one measurement (baseline or follow-up) can be included in the analysis instead of discarding patients with a missing baseline measurement. The effect of the intervention will be estimated as the mean difference and 95%CI at the follow-up time.

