### **3.8.6 Duration of hospitalisation**

Duration of hospitalisation will be analysed as the time to discharge censored at 90 days or when the subject was last known to be alive and in hospital, whichever is earlier. It will be summarised using cumulative incidence functions treating mortality as a competing risk. Medians and quartiles of time to discharge will be obtained from the cumulative incidence functions. The effect of the intervention will be estimated as the hazard ratio (intervention divided by control) and its 95%CI obtained from a Cox model of the cause-specific hazard, which estimates the risk of discharge in subjects who are still alive and have not yet been discharged. Fixed effects will include the intervention and the stratification variables (time from onset and baseline NIHSS). Site will be adjusted for using a shared-parameter frailty Cox model with a random site effect. No adjusted or subgroup analyses are planned.

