**Table 14. ICH outcomes**

Outcome / analysis method	Raw counts and percentages		Unadjusted model 			Adjusted model 		
	Intensive BP lowering group	Guideline-recommended BP lowering group	OR	(95% CI)	P-value	OR	(95% CI)	P-value
sICH by Heidelberg criteria	xxx/xxx xx.x%	xxx/xxx xx.x%	xx.xx	(xx.xx to xx.xx)	0.xxx	xx.xx	(xx.xx to xx.xx)	0.xxx
sICH by NIHSS criteria	xxx/xxx xx.x%	xxx/xxx xx.x%	xx.xx	(xx.xx to xx.xx)	0.xxx	xx.xx	(xx.xx to xx.xx)	0.xxx
sICH by SITS-MOST criteria	xxx/xxx xx.x%	xxx/xxx xx.x%	xx.xx	(xx.xx to xx.xx)	0.xxx	xx.xx	(xx.xx to xx.xx)	0.xxx
Any sICH within 90 days	xxx/xxx xx.x%	xxx/xxx xx.x%	xx.xx	(xx.xx to xx.xx)	0.xxx	xx.xx	(xx.xx to xx.xx)	0.xxx
Any ICH within 7 days	xxx/xxx xx.x%	xxx/xxx xx.x%	xx.xx	(xx.xx to xx.xx)	0.xxx	xx.xx	(xx.xx to xx.xx)	0.xxx

*Programming notes:*

- repeat this table in the per-protocol population

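### SAP 3.8 restricts the ICH comparison, including the primary safety measure, to patients with a known 90-day mRS or death, although SAP 3.2 bases safety on all randomised patients

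*SAP*

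**What the plan says.** SAP 3.2 defines the ITT population as everyone randomised and adds: "This will be used as the basis to assess both efficacy and safety". It then defines the efficacy set: "The main analysis set will consist of all patients in the ITT population with a non-missing primary outcome". Known deaths count as non-missing. The per-protocol set is drawn from the efficacy set.

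SAP 2.4.2 lists ICH as a secondary outcome under five definitions. Of the Heidelberg definition it says: "This will be the primary safety measure".

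The opening sentence of SAP 3.8 assigns populations: "All secondary outcome analyses described in this section will be performed in the efficacy (primary) and PP (sensitivity) analyses sets". ICH is analysed within that section, in 3.8.2, which names no other population and states that "no subgroup or imputed analysis will be performed on this outcome". The programming note to Table 14 (ICH outcomes) asks only to "repeat this table in the per-protocol population".

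**The concern.** Early ICH status does not depend on contact at day 90. Protocol Appendix 3 asks for a follow-up scan at 24 hours in every patient, whatever the allocation. In SAP 2.4.2 the NINDS and SITS-MOST definitions are tied to 36 hours and any ICH to 7 days. (The Heidelberg entry states no window; I treat it as an early outcome, read from the same scans.) Under 3.8, a patient with an observed, adjudicated, non-fatal sICH is nevertheless removed from numerator and denominator if a different outcome, due weeks later, is missing.

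This is selection on a post-randomisation event that could be avoided, in the primary safety comparison of an open-label trial whose protocol (10.2) applies the ITT principle. Blinded image reading and endpoint review (Protocol 13.4 and 13.5) protect the classification of events. They do not decide who is in the denominator.

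**Working it through.** **The rules side by side.**

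| Patient | ITT (SAP 3.2, safety) | Efficacy set (SAP 3.8) | Per-protocol repeat |
|---|---|---|---|
| sICH, died, death known | in | in | in, if no violation |
| sICH, alive, 90-day mRS obtained | in | in | in, if no violation |
| sICH, not known dead, 90-day mRS missing | in | **out** | **out** |

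Only the third row differs, and no planned ICH analysis brings it back.

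**Inputs from the documents.** N = 2257, 1:1 allocation, 5% loss allowance, control-arm mRS 6 = 15.3% (SAP 2.5; Protocol 6.1).

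**The plan's own figure.** This point disputes no stated number. As a check, the proportional-odds formula N = 12(z_α/2 + z_β)² / [(ln OR)²(1 − Σp̄³)], with OR 0.77, two-sided α 0.0482, 90% power and the SAP 2.5 distribution, gives 1913. Dividing by 0.95 for loss and by 0.95² for dilution from drop-in/drop-out gives 2231, which is 1.2% below 2257.

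**Assumptions not in the documents.** sICH risk p (6%, range 4-8%); fatal share f (one half, range 0-75%); 15.3% mortality in both arms; the full 5% allowance occurring as missing mRS; loss unrelated to sICH among survivors.

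**Patients excluded.** 0.05 × 2257 = 112.9, about 56 per arm, leaving about 2144.

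**Events dropped.** Only patients not known dead can be lost, and their sICH rate is p(1 − f)/(1 − 0.153).

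- p = 6%, f = 0.5: 0.03/0.847 = 3.54%. Dropped: 112.9 × 0.0354 = 4.0 of 135.4. Observed rate: (135.4 − 4.0)/2144 = 6.13%, against 6.0%.
- p = 6%, f = 0: 7.08%, 8.0 dropped, observed 5.94%.
- p = 6%, f = 0.75: 1.77%, 2.0 dropped, observed 6.22%.
- Extremes: 1.3 dropped (p = 4%, f = 0.75) and 10.7 dropped (p = 8%, f = 0).

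**Power.** Two-proportion test, two-sided 0.05, 6% against 9% (relative risk 1.5). With 1128.5 per arm: 77.2%. With 1072.1 per arm and the observed rates: 76.1% (half fatal) or 74.7% (none fatal). These figures use about 169 events in total, (6% + 9%) × 1128.5, not the 135 above.

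**Bounding case.** Take 68 events in 1128 patients per arm, 56 lost per arm, and all 4 dropped events in one arm. The OR is (64/1008)/(68/1004) = 0.94 (95% CI 0.66-1.33) where the true value is 1.00. In the other direction it is 1.07 (0.75-1.52).

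**If loss were related to sICH and differed by arm (illustration only).** With 6% sICH in each arm and 5% loss overall, 67.7 events per arm become 64.3 if 5% of sICH cases are lost. If 10% are lost in the other arm, 60.9 remain there and the OR is (60.9/1011.2)/(64.3/1007.8) = 0.94. If 20% are lost, 54.2 remain and the OR is 0.83. With half of sICH fatal, losing 20% of all cases means losing 40% of the non-fatal ones, so this is a demanding scenario.

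**The case against.** **SAP 3.2 can be read without a flat contradiction.** It calls ITT the basis for efficacy as well as safety and then defines an efficacy set inside ITT, so the word may be meant loosely. That is fair, and it makes the defect a badly chosen rule rather than two irreconcilable ones. But the loose reading still excludes the patients in question, and a programmer following 3.8 would exclude them.

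**The effect is small.** This stands. Under the base assumptions the overall rate barely moves and, with the arms alike, no between-arm distortion is expected.

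**Stronger readings that the documents do not support.**

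- A reader might infer that SAEs are restricted too, because 3.8.8 sits under the same heading. But 3.8 governs secondary outcome analyses, and 2.4.2 does not list SAEs. On the wording, the ITT safety rule of 3.2 applies to them.
- A reader might take 3.8.4 ("any patient with at least one measurement (baseline or follow-up) can be included in the analysis") and 3.8.6 ("censored at 90 days or when the subject was last known to be alive and in hospital") as proof that the intended population is unclear. Both can operate inside the efficacy set: one handles a missing scan, the other an incomplete hospital stay.
- A reader might cite SAP 3.7.4 as saying that loss is related to bleeding. It allows that some patients may be unreachable after death or serious deterioration, but it introduces this by saying that the worst-score assumption will mostly not hold. It serves to justify an mRS imputation and does not mention bleeding. A link between bleeding and loss is an inference.
- The absence of imputation for ICH is not the fault. The events at issue are observed, so imputation would not be the remedy.

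**Conclusion.** The point holds for the ICH outcomes. SAP 3.8 places the primary safety measure in a set defined by a later and different outcome, against the all-randomised basis for safety in 3.2, and it discards observed non-fatal events as a result. It should be fixed.

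The wording conclusion is firm. The size is conditional: at the 5% allowance, which is not a forecast, the loss is about 113 patients and about 4 events, with roughly one point of power. The direction of any bias is unknown. A materially distorted odds ratio would need loss that is both related to bleeding and different between arms, and nothing in the documents says that this will happen. The reason to act is that the denominator of the primary safety comparison should be right and settled before unblinding.

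**What to change.** In SAP 3.8 and 3.8.2, state that:

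1. The early ICH outcomes (Heidelberg, NINDS, SITS-MOST, any ICH within 7 days) are analysed by allocated arm in all randomised patients with ICH ascertainment, whether or not a 90-day mRS exists. The number lacking follow-up imaging is reported by arm.
2. For sICH within 90 days, all recorded events in randomised patients are included and incomplete 90-day follow-up is reported by arm, with a note that patients lost early are not known to be event-free.
3. The 7-day NIHSS, imaging and hospital-stay analyses are likewise not conditioned on the 90-day mRS.
4. The efficacy set is kept for the 90-day mRS outcomes.

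In 3.8.8, add only a clarifying note that the ITT safety rule of 3.2 applies to SAEs. Tables 14 and 15 already have places for denominators; only the population behind them needs to be stated.

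The cost is SAP wording and programming notes before unblinding, with no new data and no change to the sample size. Reporting incomplete follow-up by arm discloses the remaining gap in the 90-day outcome but does not remove it.
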